TNF inhibitors are an FDA approved class of medications indicated for the treatment of RA when initial treatment (usually with methotrexate) has failed to achieve remission of RA disease activity. TNF inhibitors are part of the standard of care management of RA. It is estimated that currently up to 20% of patients with RA are being treated with TNF inhibitors. More than 10 years of experience with these agents support the use of these agents for RA patients who do not respond to initial treatment. While TNF inhibitors have revolutionized the treatment of articular RA, their effects on heart failure (HF) has not been elucidated. Clinical trials in non-RA patients with advanced HF showed that these medications are not beneficial and may even be detrimental. Even though similar robust studies have never been performed in RA patients, product information sheets for all of the TNF inhibitors warn against their use in RA patients with advanced HF. However, their use is allowed for the treatment of RA in patients with moderate or mild HF with careful monitoring. Animal data, recent RA cohort data, and our preliminary data in RA patients suggest that TNF

inhibitors may prevent HF and/or improve LV function in RA. So far, no studies have investigated the direct effect of this class of drugs on myocardial function and structure. The hypothesis that TNF inhibitors may have a differential effect on the failing myocardium - depending on whether patients have RA or not - would reconcile the contradictory literature. Assuming that systemic or myocardial inflammation may be the primary force leading to HF in RA, we hypothesize that TNF inhibitors may be beneficial in preventing or improving HF in patients with RA. We will address this hypothesis first by examining the effect of TNF inhibitor treatment in RA patients without heart failure. If safe, further studies can direct attention to RA patients with heart failure.

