We expect that the vast majority of the 150 enrolled patients will already be on treatment with methotrexate at the time of enrollment. Methotrexate is the cornerstone of treatment for RA and almost all patients are started on methotrexate upon diagnosis of RA as part of standard of care. However only approximately 50% of patients reach a state of RA remission or low disease activity with methotrexate. The other 50% of patients with RA do not respond adequately to methotrexate and need treatment with additional agents in order to reach remission or low disease activity. In usual care patients who do not respond to methotrexate are frequently prescribed medications such as sulfasalazine and plaquenil in addition to methotrexate (triple therapy) or a TNF inhibitor in addition to methotrexate. Whether a patient receives one (TNF inhibitor) or the other (triple therapy) treatment is a matter of physician and patient preferences most of the time. Published guidelines provide only initial treatment recommendations (for example: methotrexate for all RA patients once diagnosis is established) and do not comment on whether one therapeutic agent should be preferred over an other for patients who do not respond to methotrexate (1).

For aim 2, we will identify 50 of the patients enrolled in aim 1 who are in need for further treatment due to increased RA activity despite methotrexate treatment. These patients will be recruited to continue in the study for an additional 24 (+/- 2) weeks (6 months). The patients will be randomized to receive one of the FDA approved options in an open label protocol for increased disease activity; either a TNF inhibitor or triple therapy and in the context of standard of care as already noted above. For more information regarding inclusion/exclusion criteria please refer to the appropriate IRB/RASCAL application section below.

Although treatment with TNF inhibitor and methotrexate is slightly superior in slowing radiographic joint damage, triple therapy has comparable efficacy and multiple clinical trials (COBRA and Best) robustly support the ability of the regimen to effectively reduce disease activity and slow radiographic damage (2,3).

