After the escalation in their treatment at baseline (Study Visit I) these patients will return for a second (24 weeks) study visit respectively and the set of evaluations shown in the table below - and in more detail in Appendices I, II and III - will take place. A window of +/- 2 weeks will be allowed in scheduling the study visits.

Visit II	
Evaluations	Mar/2012-Jan/2015
Cardiac PET-CT scan*	X
3D Echocardiogram	X RA &
CV Questionnaires	X
Joint examination	X
DEXA scan (body composition)	X
Phlebotomy	X
Anthropometry	X

\*including 3 transverse CT slices (mid-chest, L4-L5, mid-thigh) and low dose radiation chest CT

During PET-CT scans a low dose CT imaging of the chest is always obtained for attenuation correction as part of the usual PET-CT protocol. Although we will not need a repeat coronary artery calcium score at visit 2, low dose radiation CT imaging of the chest is always obtained for attenuation correction as part of the usual PET protocol. During this CT imaging acquisition 3 additional slices (CT cuts) will be again obtained (mid chest, lumbar, and mid thigh) to evaluate for change in visceral fat following treatment initiation.

The 3-dimensional Echocardiogram (3D Echo) will be performed to provide a measure of LV mass and will be performed in every study visit.

The 15 controls will also be asked to have a repeat set of evaluations 6 months (24 +/- 2 weeks) after their first evaluation without any therapeutic or other intervention in between the two visits. The inclusion of non-RA controls will provide important data on the normal variation of cardiac PET-CT and 3D Echo parameters over time. Further evaluations for the control participant visits are outlined in appendices I, II and III.

Every subject (RA patient or non RA control) will have a urine pregnancy test prior to tests involving radiation exposure (PET-CT scan and DEXA) and on the same day.

The screening and consent process of a patient to receive randomized escalation of treatment will be made at the time they are consented for the first study visit. It is possible that all 150 patients will qualify for randomization of their treatment but only the first 50 of those will be selected to return for study visit II. The rest of the patients will exit the study and will continue their regular care with escalation of their treatment by their treating rheumatologist outside the study.

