Linear mixed effects (MIXED) regression models will be used to assess trends in LV structure and functional outcomes over time between the two visits for the patients who will undergo randomization reevaluation with PET-CT and 3D Echocardiogram, while controlling for potential confounders. The data will include PET-CT studies for 25 RA patients receiving TNF antagonists and 25 RA patients receiving alternative treatment, and PET-CT studies for 15 non-RA patients. The data are longitudinal since LV outcomes are measured for each person at 2 different time points. Since repeated measures tend to be correlated within a person, mixed models with both fixed and random effects will be used to adjust for this correlation. We will use unstructured correlation structure given that each visit will occur roughly around a fixed time since study visit I, and use robust standard error estimates to conduct statistical inferences. To study the TNF inhibitor effects on LV structure or functional outcomes, visit-specific indicators, RA status, TNF treatment status, and visit x TNF treatment interaction will form the bases for the mean model. The visit-specific indicators will capture the time trend of LV outcomes over the study period, the RA status will delineate the overall mean difference in LV outcomes between RA and non-RA, with the TNF treatment status indicator and its interaction with visit indicators capturing the baseline difference in LV outcomes between TNF treated and non-treated groups and the potential TNF treatment effect on LV outcome over time, respectively. Actual TNF inhibitor dosage could be used in place of TNF status indicator in the model if necessary, and other potential covariates could be added into the model for confounding adjustment. For example, inflammation markers could be added into the model to examine whether any TNF treatment effect is mediated through the change in systemic inflammation. Similar modeling approaches can be used to study all research questions of interest using the corresponding outcomes and their hypothesized predictors listed in those questions to be addressed. For any binary outcomes in this type of regression analysis, e.g. indicator of whether a LV outcome exceeding certain critical value, generalized linear mixed effects models (GLIMMIX) can be used to study the odds of such outcome as a function of the independent variables.

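### The aim 2 mixed model has no visit-by-RA-status term, so its treatment coefficient compares TNF inhibitor with a pool of triple-therapy patients and untreated non-RA controls

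*Combined protocol and SAP*

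**What the plan says.** The statistical part of section 2a (Study Design) describes one linear mixed model for the two-visit data. The data comprise 25 patients on TNF inhibitors, "25 RA patients receiving alternative treatment, and PET-CT studies for 15 non-RA patients". The mean model is given as follows: "visit-specific indicators, RA status, TNF treatment status, and visit x TNF treatment interaction will form the bases for the mean model".

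The plan then assigns each term a role. "The visit-specific indicators will capture the time trend of LV outcomes over the study period, the RA status will delineate the overall mean difference" between RA and non-RA. The TNF indicator and its interaction with visit are said to capture, respectively, the "baseline difference in LV outcomes between TNF treated and non-treated groups and the potential TNF treatment effect on LV outcome over time". Inference uses an unstructured within-person correlation and robust standard errors. Covariates may be added for confounding or mediation, and "Similar modeling approaches can be used to study all research questions of interest using the corresponding outcomes and their hypothesized predictors".

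The aim 2 research questions in section 2a ask whether the effect of TNF inhibitors differs from that of alternative therapy. They draw a mechanistic conclusion if improvement is seen with TNF inhibitor alone. Section 2b reports power for a 27 g difference in LV mass between the TNF and triple-therapy arms.

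**The concern.** RA status is a constant shift across visits and is not crossed with visit. Only TNF-treated patients get their own time trend, so everyone else shares one. That remainder is a mixture of a randomised arm on active treatment and a non-randomised group without RA, studied "without any therapeutic or other intervention in between the two visits".

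The plan's own premises make unequal change in those two groups a realistic case. It says that "triple therapy has comparable efficacy and multiple clinical trials (COBRA and Best) robustly support the ability of the regimen to effectively reduce disease activity". It motivates the trial by "Assuming that systemic or myocardial inflammation may be the primary force leading to HF in RA". If both hold, triple therapy may change the myocardium while controls stay as they were.

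An equal benefit in both RA arms would then be partly credited to TNF inhibition, which is the finding the plan would read as a TNF-specific mechanism. If triple-therapy patients worsened relative to controls, a true TNF advantage would be understated. Robust standard errors do not help, because the error is in the mean model.

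**Working it through.** **Inputs.** Group sizes 25/25/15 (section 2a). Stroke volume (SV) SD 4.2 mL/m², between-visit correlation 0.2, 15% dropout, and a planning change of 5.2 mL/m² (section 2b). LV mass SD 27 g in RA and 40 g in normal people, correlation 0.35 (section 2b). Two-sided alpha 0.05. Applying each correlation to all three groups is an assumption. The triple-therapy changes below are also assumptions, because the documents give none.

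**Step 1: the plan's pairwise figure.** SD of LV mass change = 27 × √(2 × (1 − 0.35)) = 30.8 g. SE of the difference at 25 v 25 = 30.8 × √(2/25) = 8.71 g. For 27 g, a two-sided t-test has 86.0% power, in line with the more than 85% stated in section 2b. The match is not unique, since that sentence gives neither alpha nor SD. The comparison it powers is nevertheless TNF v triple therapy alone.

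**Step 2: what the listed coefficient estimates.** Write the mean as b0 + b1·visit + b2·RA + b3·TNF + b4·visit·TNF. The mean changes are then:
- TNF inhibitor: b1 + b4
- triple therapy: b1
- controls: b1

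There are six cell means but five parameters. With complete data, generalised least squares estimates b1 as the size-weighted mean change of the pooled groups, whatever the correlation:

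b4 = TNF change − (25 × triple change + 15 × control change)/40

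= (TNF change − triple change) + 0.375 × (triple change − control change)

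The control weight is 13/34 = 0.382 at 21/21/13 and 13/35 = 0.371 at 22/22/13.

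**Step 3: solving the model on cell means (25/25/15, SV in mL/m²).**

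| Change: TNF / triple / control | True TNF − triple | As listed | With visit × RA |
|---|---|---|---|
| 5.2 / 0 / 0 | 5.2 | 5.2 | 5.2 |
| 5.2 / 2 / 2 | 3.2 | 3.2 | 3.2 |
| 5.2 / 2.6 / 0 | 2.6 | 3.575 | 2.6 |
| 5.2 / 5.2 / 0 | 0 | 1.95 | 0 |

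**Step 4: false-positive rate.** Assume equal change in both RA arms (true contrast 0), no change in controls, and 21/21/13 after dropout. The listed model with robust SE was simulated 6,000 times per scenario.

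| Outcome | Common change | Spurious TNF effect | Rejection |
|---|---|---|---|
| SV, mL/m² | 0 | 0 | 6.4% |
| | 1 | 0.4 | 6.9% |
| | 2 | 0.8 | 9.5% |
| | 3 | 1.1 | 13.2% |
| | 5.2 | 2.0 | 25.9% |
| LV mass, g | 0 | 0 | 6.0% |
| | 5 | 1.9 | 6.6% |
| | 10 | 3.8 | 8.3% |
| | 20 | 7.6 | 13.7% |
| | 27 | 10.3 | 19.4% |

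The last row of each block is upper-end: it gives triple therapy the full change used to plan for TNF. With visit × RA added, null estimates are about 0 and robust rejection is 6.0–6.7% for both outcomes.

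**Step 5: opposite direction.** Let TNF truly be 5.2 mL/m² better than triple therapy, with controls unchanged. If triple therapy changes by −2, the listed estimate is about 4.4 (power 86%, against 89% with the term added). At −5.2, again upper-end, it is 3.2 (57% against 90%).

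**The case against.** The strongest reply is that the paragraph gives a starting set of terms, not a closed model. It calls the terms the basis of the mean model, allows additions, and extends similar modelling to every research question. A correct contrast is therefore permitted. Elsewhere the arms are kept apart: section 2b treats TNF, triple therapy and controls as three groups in its ANOVA, and initial t-tests are allowed. A t-test of change between the two randomised arms would be unbiased. Section 2b's SV scenario sets the change to 0 in both other groups; there the bias is zero and pooling gains power.

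Much of this is fair, but it does not replace the listed coefficient. The power statements and the generic t-test provision do not specify a TNF-versus-triple test of change, and no text calls for visit × RA. Zero change in both groups is a planning scenario, not evidence. Covariates fixed over time would not undo the pooling. Inflammation markers entered at both visits might let the trends differ, but that is adjustment for a mediator.

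Two points on size stand. Only about 38% of any triple-versus-control difference in change leaks into the estimate, and at modest changes the extra rejection is small: about 1–3 points for SV at 1–2 mL/m², and 0.5–2 points for LV mass at 5–10 g. A finding of improvement with TNF inhibitor alone would also need the triple-therapy change itself, which the study will collect, so an attentive reader of the group means could see the problem.

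**Conclusion.** The concern holds. Followed as written, the only coefficient the plan describes as the treatment effect does not isolate the randomised comparison. Its bias is 0.375 × (triple-therapy change − control change) with complete data, in either direction. That result is algebraic and does not depend on the illustrations. Dropout alters the weight slightly (0.371 to 0.382 in the cases above).

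The practical size is uncertain because it depends on a triple-therapy change that the documents do not give. For SV it runs from negligible (about 7% rejection at a common change of 1 mL/m²) to serious (about 26% at 5.2 mL/m²), against about 6% with no bias. The wording does not forbid a correct model, but it does not specify one. Since this is the trial's only randomised comparison and the remedy is a change of wording, it should be corrected before analysis.

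**What to change.** - Replace the listed mean model with a three-level group (TNF inhibitor, triple therapy, non-RA control) crossed with visit. Equivalently, add visit × RA status, or fit the model in the 50 randomised patients only.
- Name the difference in mean change, TNF inhibitor minus triple therapy, as the treatment-effect test.
- Use the controls to describe normal variation over time, which is the purpose section 2a gives for including them.
- If controls stay in the model, keep the planned robust SE. With a control SD of 40 g, the model-based test of LV mass with one pooled covariance is conservative (2.6–2.9% rejection instead of 5%).

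**Cost.** No change to data collection. With equal SDs the SE rises by √(1/25 + 1/25) / √(1/25 + 1/40) = 1.109, about 11%. For LV mass with control SD 40 g it rises from 8.50 to 8.71 g, about 2.5%. If triple therapy and controls both stay unchanged, SV power at 5.2 mL/m² is 87.2% (21 v 21) instead of 93.3% (21 v 34), still above 80%.

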## 2. STUDY DESIGN AND STATISTICAL PROCEDURES

### 2a. Study Design

(this section includes references)

For aim 1, the proposed studies will be performed in 150 patients with RA and 15 subjects without RA who will function as controls. The 150 patients will be recruited from the rheumatology clinics at New York Presbyterian Hospital of the Columbia University. The 15 control subjects will be recruited from the internal medicine clinics at the same institution or among friends of the recruited RA patients.

The 150 participants should have RA fulfilling established diagnosed criteria and not have a history of cardiovascular disease as indicated in the section for inclusion/exclusion criteria

[figure not shown]
These patients (150) will undergo the evaluations shown in the table below - and in more detail in Appendices I, II and III - during an initial visit (Visit I).

Evaluations	Visit I September/2011 - August/ 2014
Cardiac PET-CT scan*	X
3D Echocardiogram & CV Questionnaires	X RA X
Joint examination	X
Phlebotomy	X
Anthropometry	X
DEXA scan (body composition)**	X

\*including 3 transverse CT slices (mid-chest, L4-L5, mid-thigh) and cardiac CT for evaluation of coronary artery calcification (CAC).

\*\*only for the 50 participants who will be recruited for aim 2. (see below)

During the first PET scan a cardiac CT scan will be obtained in order to quantify coronary artery calcium (Agatston Score). Three additional CT Slices will be obtained (mid chest, lumbar, and mid thigh) to evaluate for visceral fat

accumulation as a risk factor for cardiovascular disease.

Controls will undergo only the PET-CT scan, 3D Echo, anthropometry evaluations, phlebotomy, and will complete abbreviated cardiovascular related questionnaires as outlined in Appendices I, II and III.

The PET-CT scan will occur on the same day or within one week of Study visit I.

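### The RA-status term of the aim 2 mixed model is not the overall RA versus non-RA difference: it is triple-therapy patients minus controls, combined over both visits

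*Combined protocol and SAP*

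**What the plan says.** The mixed-model paragraph of section 2a covers "25 RA patients receiving TNF antagonists and 25 RA patients receiving alternative treatment" and "PET-CT studies for 15 non-RA patients", each measured at two visits. It lists the fixed effects: "visit-specific indicators, RA status, TNF treatment status, and visit x TNF treatment interaction will form the bases for the mean model". It then interprets them. RA status is given the meaning "the RA status will delineate the overall mean difference in LV outcomes between RA and non-RA". The TNF indicator and its interaction with visit are read as "capturing the baseline difference in LV outcomes between TNF treated and non-treated groups" and as the treatment effect over time. On the covariance it says "We will use unstructured correlation structure". No visit by RA term is listed.

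The same section says of aim 1 that "the proposed studies will be performed in 150 patients with RA and 15 subjects without RA who will function as controls". RA patients outside the randomized part are seen at Visit I only. Controls return after about 24 weeks with no intervention in between, while the randomized RA patients have had their treatment escalated by then.

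**The concern.** Because the TNF main effect is read as a baseline difference, TNF status must be a fixed arm indicator. The two TNF-arm means then have two parameters that appear nowhere else, and the RA coefficient has to be estimated from the other two groups. Because RA does not interact with visit, that coefficient is also forced to be the same before and during treatment.

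The mixed-model paragraph is the only model description that gives a term an RA versus non-RA meaning, and lower LV mass in RA is the background premise of the study (section 1). An analyst who follows the text would call a contrast of 25 partly treated RA patients with 15 controls the overall RA difference.

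**Working it through.** **Inputs.** Group sizes are 25 TNF, 25 triple therapy and 15 controls (section 2a). LV mass is 120 g (SD 27) in RA and 147 g (SD 40) in normal people, and the within-person correlation is r = 0.35 (section 2b). The plan gives no Visit II SDs, so unequal visit SDs below are assumptions. Data are taken as complete at both visits. The plan states no figure for this coefficient, so there is none to reproduce.

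**Step 1: the model in cells.** Write the mean as b0 + b1·visit + b2·RA + b3·TNF + b4·visit·TNF.

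| Group | Visit I | Visit II |
|---|---|---|
| Control | b0 | b0+b1 |
| Triple | b0+b2 | b0+b1+b2 |
| TNF | b0+b2+b3 | b0+b1+b2+b3+b4 |

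b3 and b4 occur only in the TNF row and fit its two means exactly. Those means therefore carry no weight in b2; TNF-arm data help only to estimate the covariance. In a mixed model fitted to one simulated data set, adding 50 g to every TNF Visit II value left b2 unchanged at -25.63 g, which equals triple minus control averaged over the two visits.

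**Step 2: what b2 combines.** Let D1 and D2 be triple minus control at Visits I and II. Both estimate b2, and generalized least squares gives b2 = w1·D1 + w2·D2, with w1 = 1 - w2 and

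w2 = (s1² - c)/(s1² + s2² - 2c), c = r·s1·s2.

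So b2 has expectation D1 + w2 × (triple change - control change).

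**Step 3: the share absorbed.**
- Equal visit SDs: w2 = 0.5 at any r below 1.
- SDs 27/32 g, r = 0.35: c = 302.4, so w2 = (729 - 302.4)/(1753 - 604.8) = 0.37.
- SDs 27/32 g, r = 0.7: w2 = 0.23.
- SDs 27/40 g, r = 0.35: w2 = 0.22. Reversed, 40/27 g: w2 = 0.78.

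**Step 4: size for LV mass.** Take D1 = 120 - 147 = -27 g and stable controls.
- Triple change 0: -27 g.
- Triple rise of 13.5 g, equal SDs: -27 + 0.5 × 13.5 = -20.25 g.
- The same rise with w2 = 0.22, 0.37 or 0.78: about -24.0, -22.0 or -16.5 g.
- A TNF-arm change of 0 or 27 g makes no difference to any of these.

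**Step 5: precision.** With the plan's SDs and equal visit variances, the factor for averaging two visits is (1 + 0.35)/2 = 0.675.
- Planned coefficient: √[0.675 × (27²/25 + 40²/15)] = √[0.675 × 135.83] = 9.6 g.
- Visit I regression, 150 versus 15, unadjusted: √[27²/150 + 40²/15] = √111.53 = 10.6 g.
- Cost of leaving out the TNF arm at Visit I, common SD 27 g: 27·√(1/25 + 1/15) = 8.82 g against 27·√(1/50 + 1/15) = 7.95 g.

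**The case against.** The paragraph introduces this model to study TNF inhibitor effects, so RA status is there as an adjustment term. None of the listed research questions asks for an RA versus non-RA difference in LV mass, and the controls' stated purpose is to show normal variation over time. The listed terms are only the basis of the model: covariates may be added, and dose may replace the TNF indicator, which would change the weights. The word *overall* might mean averaged over visits. These points limit what is at stake. They do not rescue the label, because averaging over visits does not bring the TNF arm back in, and no added term is specified that would restore the stated meaning.

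The plan's own scenarios also give no bias. Section 2b has the TNF arm rising from 120 to 147 g and differing from triple therapy by 27 g, which implies no triple-arm change. Its stroke-volume scenario sets the change in the other two groups to zero. That stands: the 13.5 g rise above is an illustration, not a planning assumption.

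Stronger readings that a reader might infer are not supported:
- *The coefficient absorbs half of any treatment change.* TNF-arm change does not enter at all, and the triple-arm share is half only with equal visit variances.
- *It ignores 125 of the 150 RA patients.* The arithmetic is right, but 100 of these have no Visit II and lie outside this model by design. Inside the model, 25 of 50 carry no weight.
- *Chance baseline imbalance makes it seriously misleading.* Randomization equalizes the arms in expectation. A split such as 110 g versus 130 g is 20/(27·√(2/25)) = 20/7.6 = 2.6 standard errors, an extreme event.
- *It will be the reported RA deficit.* Nothing in the document names it as a reported result.

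**Conclusion.** The point holds as a mislabelled coefficient. As specified, the RA term estimates triple therapy minus control combined over an untreated and an on-treatment visit, not the overall RA versus non-RA difference. That follows from the listed terms alone and does not depend on the variances.

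The size does depend on assumptions. There is no systematic bias if the triple arm changes no more than the controls. Otherwise the bias is the relative change times a share that is 50% with equal visit variances and ran from 22% to 78% over the SDs assumed here. With a stable triple arm, the only loss is the precision of the unused TNF baseline data. The point does not show that a wrong RA result will be published; it shows that the text invites a wrong interpretation, which is worth correcting before analysis.

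**What to change.** In the mixed-model paragraph of section 2a, delete the reading of RA status as the overall RA difference. Describe it instead as an adjustment term: triple therapy minus control, averaged over visits (with weights that depend on the fitted covariance).

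Wherever an RA versus non-RA difference is to be reported, specify a separate Visit I regression of all 150 RA patients and 15 controls, adjusted for the conventional CV risk factors that section 2a already names for the aim 1 models. This population is broader than the randomized 50, for whom diabetes and smoking are exclusions, and the text should say so.

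The cost is one extra regression and one changed sentence, with no new data. It is not free in precision: with the plan's SDs the LV mass SE is about 10.6 g against 9.6 g, because one visit is used instead of two and the 15 controls dominate the variance. The change leaves the visit by TNF term as it is; that term is outside this point.
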